7.1.4.3 Long-term Follow-up / Trial Termination

All SAEs ongoing at the 28-Day Safety Follow-up visit must be monitored and followed up by the Investigator until stabilization or until the outcome is known, unless the subject is documented as “lost to follow-up”. In addition, all trial drug-related SAEs occurring after 28-Day Safety Follow-up visit and ongoing at the Safety Follow-up visit have to be followed up in the same manner.

Subjects without PD at the 28-Day Safety Follow-up visit will be followed up for disease progression (CT / MRI scans every 12 weeks with the first assessment 12 weeks after the previous tumor assessment [scheduled time point]) until PD.

After the 28-Day Safety Follow-up visit, subjects will be followed quarterly (\pm 14 days) for survival (including assessment of any further anticancer therapy). The survival follow-up will continue until 1 year after the last subject receives the last dose of MSB0011359C.

After completion of the Follow-up period or at discontinuation of the trial, whatever is applicable / comes first, the appropriate eCRF section for Trial Termination must be completed.

7.1.5 Blood Consumption for Clinical Assessments

The overall amount of blood to be drawn from a single subject must not exceed 120 mL/day and 550 mL in an 8-week period for safety laboratory testing, pregnancy testing, PK analyses, CCI, and antibody evaluation.

7.2 Demographic and Other Baseline Characteristics

The assessments and procedures described in this section must be performed during the Screening period.

7.2.1 Demographic Data

The following demographic data will be recorded:

- Subject identifier
- Date of birth
- Sex
- Ethnicity
- Race.

7.2.2 Diagnosis of Tumor

The tumor disease information that will be documented and verified at the Screening visit for each subject includes:

- Detailed history of the tumor, including histopathological diagnosis, grading and staging in accordance with the Union Internationale Contre le Cancer Tumor Node Metastasis Classification at diagnosis (UICC TNM)
 - The M category (M0 or M1) of the tumor at the time of study entry, based on screening assessments
- All therapy used for prior treatment of the tumor (including surgery, radiotherapy and chemotherapy, immunotherapy, etc)
- Any other conditions that were treated with chemotherapy, radiation therapy, or immunotherapy
- Current cancer signs and symptoms and side effects from current and / or previous anticancer treatments
- Current cancer disease status
- BRCA, tumor HPV and tumor mismatch-repair status documentation, if known
- Smoking history (for NSCLC and cervical cancer expansion cohorts only).

7.2.3 Medical History

In order to determine the subject's eligibility to the trial, a complete medical history of each subject will be collected and documented during Screening, which will include, but may not be limited to, the following:

- Past and concomitant non-malignant diseases and treatments
- All medications taken and procedures carried out within 30 days prior to Screening

For the trial entry, all the subjects must fulfill all inclusion criteria described in Section 5.3.1, and none of the subjects should have any exclusion criterion from the list described in Section 5.3.2.

7.2.4 Vital Signs and Physical Examination

Vital signs including body temperature, respiratory rate, heart rate (after 5-minute rest), and arterial blood pressure (after 5-minute rest), body weight and height will be recorded at study entry.

Physical examinations will be performed according to Table 1 and Table 2. An ophthalmology examination including slit lamp evaluation inclusive of the anterior segment and with visual acuity should be conducted.

The ECOG PS will be documented during the Screening phase.

7.2.5 CT or MRI Scans for Tumor Assessment at Baseline

A CT scan or MRI (if MRI is used, CT of chest is mandatory [for trial sites in countries with radiation exposure control for subjects, only MRI may be used]; for subjects in the HCC cohort, multiphase CT with contrast is mandatory) of the chest, abdomen, and pelvis (at a minimum and other established assessments of tumor burden if CT / MRI imaging is not sufficient for the individual subject; other regions as specifically required for specific tumor indications) will be performed within 28 days prior to trial treatment start in order to document the baseline status of the tumor disease using RECIST 1.1 target and non-target lesions and secondarily using mRECIST for subjects in the HCC cohort (see vendor manual). For subjects in the glioblastoma cohort, the assessment will be made according to RANO. However, if the results of a CT scan or MRI performed within 4 weeks prior to first treatment are available, the Screening CT / MRI does not need to be performed.

A brain CT / MRI scan (either, contrast preferred) is required at Screening if not performed within the previous 6 weeks. Thereafter, brain CT / MRI scan should be done if clinically indicated by development of new specific symptoms.

A bone scan should be done at Screening as clinically indicated.

7.2.6 Cardiac Assessments

A 12-lead ECG will be recorded at Screening. The ECG will be recorded after the subject has been in a supine position breathing quietly for 5 minutes. The ECG results will be used to evaluate

the heart rate, atrial-ventricular conduction, QR, QT, and corrected QT intervals, and possible arrhythmias.

The dose escalation and NSCLC biomarker cohorts must utilize digital ECGs. The ECGs will be documented by recording date and time of collection. All ECG results must be reviewed at the site by the Investigator or a medically qualified designee for clinical management of the subject. The digital ECGs will also be electronically transferred to the central ECG laboratory to be read by a cardiologist. The result of the central read will be used for statistical evaluation of ECG data. For the NSCLC biomarker cohort, all ECGs after Week 13 are single ECGs obtained according to local procedure and will NOT be digitally uploaded. For all other expansion cohorts, ECGs are to be performed according to local procedures and will NOT be digitally uploaded.

Digital ECG uploading and central reading will not be used for the remaining expansion cohorts.

The Investigator will judge the overall interpretation as normal or abnormal. If abnormal, it will be decided if the abnormality is clinically significant or not clinically significant and the reason for the abnormality will be recorded on the eCRF. Abnormal values will not be recorded as AEs unless they are the reason for discontinuation of the trial IMP due to AEs or are SAEs.

7.2.7 Clinical Laboratory Tests

Blood samples will be collected at Screening for clinical laboratory parameter evaluations. These clinical laboratory test results will serve not only as the baseline values for subsequent safety clinical laboratory evaluations during the trial, but also help to make sure that each enrolled subject fulfills all the trial entry criteria as listed in Section 5.3.1 and does not meet any of the trial exclusion criteria for laboratory parameters as listed in Section 5.3.2. Detailed description of laboratory assessments is provided in Section 7.4.3.

7.3 Efficacy Assessments

For all subjects in all cohorts, tumor response assessment will be performed by CT scan or MRI (if MRI is used, CT of chest is mandatory [for trial sites in countries with radiation exposure control for subjects, only MRI may be used], for subjects in the HCC cohort, multiphase CT with contrast is mandatory) imaging of the chest / abdomen / pelvis (plus other regions as specifically required for specific tumor types) and other established assessments of tumor burden if CT / MRI imaging is insufficient for the individual subject. All the scans performed at Baseline and other imaging performed as clinically required (other supportive imaging) need to be repeated at subsequent visits. In general, lesions detected at Baseline need to be followed using the same imaging methodology and preferably the same imaging equipment at subsequent tumor evaluation visits.

A brain CT / MRI scan (either, with contrast preferred) is required at Screening if not performed within the previous 6 weeks. Thereafter brain CT / MRI scan should be performed, if clinically indicated by development of new specific symptoms. A bone scan should be performed at Screening and beyond as clinically indicated. Skin metastasis can be used as target lesions according to RECIST 1.1 using measurements by caliper, if they fulfill RECIST 1.1 for target lesions as described below. The presence of new cutaneous lesions will be considered diagnostic of progression for RECIST 1.1, even if not imaged. For each subject, the Investigator will

designate 1 or more of the following measures of tumor status to follow for determining response: CT or MRI images of primary and / or metastatic tumor masses, physical examination findings, and the results of other assessments. All available images collected during the trial period will be considered. The most appropriate measures to evaluate the tumor status of a subject should be used. The measure(s) to be chosen for sequential evaluation during the trial have to correspond to the measures used to document the progressive tumor status that qualifies the subject for enrollment. The tumor response assessment will be assessed and listed according to the Schedule of Assessments (refer to [Table 1](#) and [Table 2](#)).

The foreseen treatment duration is until disease progression verified by a scan subsequent to the initial documentation of PD, unacceptable toxicity, or any criterion for withdrawal from the trial or IMP occurs (see Section 5.5). **Before stopping the treatment, progressive disease should be confirmed by imaging 4 to 6 weeks (preferably 6 weeks, but not later) after progression has been diagnosed according to RECIST 1.1.** If progression is based on the occurrence of a new lesion in an area not scanned at Baseline, a further on-study scan 6 weeks later should be considered before performing the 28-Day Safety Follow-up visit. Treatment may be continued despite progression according to RECIST 1.1 at any time if:

- There are no new symptoms or worsening of existing symptoms.
- There is no decrease in ECOG PS.
- The Investigator does not consider it necessary to administer a salvage therapy.

The treatment should be stopped immediately, if the subject does not tolerate MSB0011359C anymore or if therapeutic failure occurs, which requires urgent treatment with an additional drug or results in clinically significant progression / deterioration.

Tumor responses to treatment will be assigned based on the evaluation of the response of target, non-target, and new lesions according to RECIST 1.1 (all measurements should be recorded in metric notation) and secondarily using mRECIST for subjects in the HCC cohort (see Section 7.3.2). For subjects in the glioblastoma cohort, the assessment will be made according to RANO.

- To assess objective response, the tumor burden at baseline will be estimated and used for comparison with subsequent measurements. At baseline, tumor lesions will be categorized in target and non-target lesions according to RECIST 1.1 and secondarily using mRECIST for subjects in the HCC cohort. For subjects in the glioblastoma cohort, the assessment will be made according to RANO.

Results for these evaluations will be recorded with as much specificity as possible so that pre- and post-treatment results will provide the best opportunity for evaluating tumor response.

Any CR or PR should be confirmed according to RECIST 1.1 or RANO for subjects with glioblastoma. **In the case of a PR or CR, a confirmatory CT or MRI scan must be done no sooner than 4 weeks (preferably at the scheduled 6-week interval).**

The Investigator may perform scans in addition to a scheduled trial scan for medical reasons or if the Investigator suspects PD.

As outlined in Section 5.1, treatment should continue with the investigational drug and the subject may remain on study according to the Investigator's decision and in agreement with the subject in case of PD according to RECIST 1.1, mRECIST (HCC), or RANO (glioblastoma).

Subjects who have experienced SD, PR, or CR should continue treatment through the end of 12 months, although additional treatment is possible. If the Investigator believes that a subject may benefit from treatment beyond 12 months, it may be permissible after discussion with the Medical Monitor and the Sponsor Medical Responsible. Subjects re-initiating treatment should be assessed according to the Schedule of Assessments (see Section 5.1.6).

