3.5.3 TGF β Inhibition Mediated Skin Reactions

Skin AEs, possibly due to TGF β inhibition, including hyperkeratosis, KA, and/or cSCC, are AESIs and important identified risks for MSB0011359C. The distribution of lesions tends to be in sun exposed areas.

For nonserious AESIs, an AESI Report Form has to be completed; for serious events, an SAE Report Form has to be used (see Section 7.4.1.4).

See Section 6.5.4 for risk management measures for TGF β inhibition mediated skin reactions.

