- Increases in Eastern Cooperative Oncology Group performance status (ECOG PS) \geq 3 that resolves to \leq 2 by Day 1 of the next cycle (infusions should not be given if the ECOG PS is \geq 3 on the day of IMP administration and should be delayed until ECOG PS \leq 2).
- Keratoacanthoma and squamous cell carcinoma of the skin. Any suspicious skin lesion should be biopsied and be surgically removed. The Study Medical Monitor should be consulted.
- Grade 3 or 4 dermatological irAEs, treatment should be delayed and treatment started according to [Table 7](#), if condition improves to Grade 1, treatment may be resumed. If \geq 2 consecutive doses are missed, the Medical Monitor should be consulted.
- Grade 3 or 4 symptomatic endocrinopathies (eg, thyroiditis or hypophysitis), treatment should be delayed and treatment started according to [Table 7](#), if condition improves to Grade 1, treatment may be resumed. If \geq 2 consecutive doses are missed, the Medical Monitor should be consulted.
- Other immune-related ADRs, see [Table 7](#).

Any Grade 2 ADR should be managed as follows:

- If a Grade 2 ADR resolves to Grade \leq 1 by the last day of the current cycle, treatment may continue.

- If a Grade 2 ADR does not resolve to Grade ≤ 1 by the last day of the current cycle but it is manageable and / or not clinically relevant, the ADR should be discussed with the Medical Monitor and based upon discussion it is possible the infusion will be given on the following cycle. If at the end of the following cycle, the event has not resolved to Grade 1, discussion should be had with the Medical Monitor about permanently discontinuing treatment with MSB0011359C.
- Upon the second occurrence of the same Grade 2 ADR in the same subject (except for fatigue and hormone insufficiencies that can be managed by replacement therapy), continuation of treatment with MSB0011359C has to be discussed with the Medical Monitor and might be permanently discontinued.
- Infusion-related reactions and hypersensitivity reactions (Grades 1 to 4) should be handled according to the guidelines provided in Sections 6.5.4.1 and 6.5.4.2, respectively.
- Anemia should be handled according to the guidelines provided in Section 6.5.4.4.
- If immune-related ADR, see Table 7.

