6.5.4.4 TGFβ Inhibition Mediated Skin Reactions

Skin assessments are performed at Screening period and every 6 weeks for all subjects per Schedule of Activities (see [Table 1](#) **Error! Reference source not found.**).

Skin AEs, possibly due to TGFβ inhibition, including hyperkeratosis, KA, and/or cSCC, are AESIs and important identified risks for MSB0011359C. The distribution of lesions tends to be in sun-exposed areas.

Management guidelines for potential TGFβ inhibition mediated skin reactions are:

1. Discontinuation or interruption is not required in most cases. Continuation of treatment should be evaluated by the Investigator.
2. Emollients may continue to be used.
3. Diagnostic and treatment plan should be developed in collaboration between Investigator and dermatologist. In general, treatment of TGFβ mediated skin lesions such as hyperkeratosis, KA and cSCC should be based on local guidelines/SoC. Lesion evaluation should include excision biopsy of one representative lesion to confirm diagnosis.
4. Treatment and Follow-up for KA and cSCC will depend on number and localization of lesions.
 - For single lesions: Full excision may be recommended.
 - In case of multiple lesions or location not suitable for full excision, other treatment options may be offered by the dermatologist, such as:
 - Mohs surgery, cryotherapy, or other standard treatment options depending on the pathology
 - Use of retinoids, if recommended by dermatologist, may be considered after discussion with Medical Monitor.
5. Close clinical Follow-up for re-evaluation, resolution, or potential recurrence should be implemented.

6. Spontaneous resolution of KA lesions without surgical intervention has been observed, typically occurring within weeks after discontinuing MSB0011359C.

Consult with study Medical Monitor, as needed, for management of TGF β mediated skin lesions.

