7.4.1.1.2 Serious Adverse Events

An SAE is any untoward medical occurrence that at any dose:

- Results in death,
- Is life-threatening (Note: The term "life-threatening" refers to an event in which the subject is at risk of death at the time of the event, not an event that hypothetically might have caused death if it was more severe),
- Requires inpatient hospitalization or prolongs an existing hospitalization,
- Results in persistent or significant disability or incapacity,
- Is a congenital anomaly or birth defect, or
- Is otherwise considered to be medically important.

Note: Important medical events that may not result in death, be life-threatening, or require hospitalization may be considered as SAEs when, based upon appropriate medical judgment, they may jeopardize the subject or may require medical or surgical intervention to prevent one of the outcomes listed above. Examples of such events include allergic bronchospasm requiring intensive treatment in an emergency room or at home, blood dyscrasias or convulsions that do not result in inpatient hospitalization, or the development of drug dependency or drug abuse. Any type of new (secondary) cancer including squamous cell cancer of the skin should be considered as medically important condition.

For the purposes of reporting, any suspected transmission of an infectious agent via an IMP is also considered a SAE, as described in Section 7.4.1.4.

Events That Do Not Meet the Definition of an SAE

Elective hospitalizations to administer, or to simplify trial treatment or trial procedures (for example, an overnight stay to facilitate chemotherapy and related hydration therapy application) are not considered SAEs. However, all events leading to unplanned hospitalizations or unplanned prolongation of an elective hospitalization (for example, undesirable effects of any administered treatment) must be documented and reported as SAEs.

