8.3 Endpoints

8.3.1 Primary Endpoints

The primary endpoints for the dose-escalation part of the trial are the:

- Number, severity, and duration of TEAEs according to the NCI-CTCAE v4.03
- Number, severity and duration of treatment-related AEs for all dose groups / indications according to CTCAE v4.03
- Occurrence of DLTs during the first 3 weeks (21 days) of treatment in the dose-escalation part of the trial

Except for the glioblastoma cohort, the primary efficacy endpoint for the dose-expansion part of the trial is the confirmed BOR according to RECIST 1.1 as adjudicated by the IRC (Section 2.2.2) and will be evaluated by confirmed ORR. For glioblastoma, the primary endpoint will be disease control according to RANO as adjudicated by the IRC.

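### Protocol 7.3 scores a new skin lesion as RECIST 1.1 progression without requiring it to be study tumor, although the drug is known to cause new skin lesions

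*Protocol*

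**What the plan says.** **The scoring rule.** Protocol 7.3: "The presence of new cutaneous lesions will be considered diagnostic of progression for RECIST 1.1, even if not imaged". The sentence before it deals with a narrower object: "Skin metastasis can be used as target lesions according to RECIST 1.1 using measurements by caliper". Later in the same section: "Tumor responses to treatment will be assigned based on the evaluation of the response of target, non-target, and new lesions according to RECIST 1.1". New lesions therefore feed directly into response. For the expansion cohorts other than glioblastoma, Protocol 8.3.1 says "the primary efficacy endpoint for the dose-expansion part of the trial is the confirmed BOR according to RECIST 1.1 as adjudicated by the IRC", evaluated by confirmed ORR.

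**The safety sections.** Protocol 3.5.3 says that skin events possibly due to TGFβ inhibition, "including hyperkeratosis, KA, and/or cSCC, are AESIs and important identified risks for MSB0011359C". Protocol 5.1.7.2 lists among the exceptions to stopping treatment for a Grade 3 reaction: "Keratoacanthoma and squamous cell carcinoma of the skin. Any suspicious skin lesion should be biopsied and be surgically removed". Protocol 6.5.4.4 says: "Lesion evaluation should include excision biopsy of one representative lesion to confirm diagnosis". Protocol 7.4.1.1.2 says: "Any type of new (secondary) cancer including squamous cell cancer of the skin should be considered as medically important condition". Protocol 5.1.3.3 also leaves a local, fully resectable malignant skin lesion out of the DLT definition.

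**The concern.** The scoring section and the safety sections can classify one and the same lesion differently. A KA that appears on treatment is an adverse event of special interest under 3.5.3 and 6.5.4.4. Read literally, it is also RECIST progression under 7.3. The biopsy that could tell the two apart is called for on safety grounds, but no text carries its result into the response assessment.

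False progression of this kind is not random noise. It arises from the drug's own mechanism and always counts against the drug. The melanoma cohort is exposed because skin is also a real site of disease. The squamous tumors (SCCHN, squamous cervical, squamous NSCLC) are exposed because a primary cSCC and a squamous skin metastasis can look alike.

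**Working it through.** **1. Does any text exclude drug-related skin lesions from the rule?** The places that might do so:

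- Protocol 7.3: the preceding sentence speaks of skin metastases; the rule itself speaks of cutaneous lesions, with no condition on histology or cause.
- Protocol Table 2, footnote s: in melanoma, on-treatment skin photographs are barred when none was taken at baseline, so that old lesions are not mistaken for new ones. This guards against a different error.
- Protocol 7.4.1.1.3: progression is generally not reported as an adverse event. This keeps the two categories apart but does not say which one a new skin lesion belongs to.
- Protocol 2.2.2: the independent review committee (IRC) also reviews physical findings. Its processes are left to a charter that was not supplied, and part of the paragraph is redacted.
- Protocol 7.1.2.2: pathology reports must be on file and open to review on request. They are not tied to response scoring.

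None of these excludes the lesions.

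**2. How would one lesion cost a confirmed response?** Tumor scans are at Week 7 and then every 6 weeks. Under Protocol 7.3 a response is confirmed at least 4 weeks after it is first seen, preferably at the next 6-weekly scan. SAP 14.1 closes the BOR window at first documented progression, and SAP 14.1.1 requires both determinations of a PR to precede progression. Suppose a subject has a PR at Week 7, a KA at Week 10 and a continuing PR at Week 13. If the KA is scored as PD, only one determination precedes progression and no confirmed PR remains. If the KA appears after Week 13, the confirmed PR stands, but PFS, TTP and duration of response end early.

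**3. Reproduce the stated power.** Inputs from Protocol 8.1.2 (n also from the Synopsis): n = 30 and one-sided α = 0.10 in both cohorts; melanoma p0 = 5%, p1 = 20%, stated power 87%; SCCHN p0 = 15%, p1 = 35%, stated power 87%. The cutoff r is the smallest count with P(X ≥ r | n, p0) ≤ α, and power = P(X ≥ r | n, p1).

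- Melanoma: P(X ≥ 3 | 0.05) = 0.1878, P(X ≥ 4 | 0.05) = 0.0608, so r = 4; power 0.8773.
- SCCHN: P(X ≥ 7 | 0.15) = 0.1526, P(X ≥ 8 | 0.15) = 0.0698, so r = 8; power 0.8762.

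Both agree with the stated 87%.

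**4. Show a range for the effect.** The documents give no rate of these lesions before confirmation. Assume that a share q of true responders is scored PD first. The effective ORR is then p1 × (1 − q), with r unchanged.

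| q (assumed) | Melanoma: ORR | Power | SCCHN: ORR | Power |
|---|---|---|---|---|
| 0 | 0.200 | 0.8773 | 0.3500 | 0.8762 |
| 3% | 0.194 | 0.8605 | 0.3395 | 0.8502 |
| 5% | 0.190 | 0.8484 | 0.3325 | 0.8308 |
| 10% | 0.180 | 0.8144 | 0.3150 | 0.7749 |

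The loss is 1.7 to 6.3 points in melanoma and 2.6 to 10.1 points in SCCHN.

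**The case against.** The best defense is context. The rule directly follows a sentence on skin metastases, and its purpose may be only to waive imaging for them. Classing cSCC as a secondary cancer, and generally keeping progression out of adverse event reporting, fit that reading. It may well be what was meant, but the wording does not say so, and an assessor who applies the sentence literally would score PD.

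Second, the primary endpoint is adjudicated by an IRC that sees physical findings, and it may discount a proven KA. This stands as a limit on certainty: without the charter, nobody can say how such lesions are scored in practice. It does not repair the written rule.

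Third, the analyses are exploratory and uncontrolled, and the error is conservative. That lowers the stakes but does not make the classification right.

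Four stronger readings are tempting and go too far:

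- *Every cohort's primary endpoint is at risk.* Glioblastoma uses RANO, dose escalation has safety primary endpoints, and elsewhere a subject loses the primary endpoint only if the lesion precedes confirmation.
- *The SAP fixes this error in the primary analysis.* The supplied SAP covers investigator-assessed efficacy in cervical cancer for a cancelled report addendum (SAP 6.1, 14). Its BOR rules show how progression cuts off response; they are not the IRC analysis.
- *Treatment would be stopped wrongly.* Protocol 7.3 asks for confirmatory imaging before stopping. The point concerns scoring only.
- *Every cSCC should be exempt from progression.* In squamous study tumors that could hide a true skin metastasis and move the bias in favor of the drug.

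**Conclusion.** The point holds as a gap in endpoint definition. As written, 7.3 can turn a recognized drug reaction into RECIST 1.1 progression in the RECIST-assessed expansion cohorts, and the supplied documents do not resolve the conflict. The direction is clear: against the drug. The size is unknown. The power figures rest on three assumptions: that 3% to 10% of would-be responders are affected before confirmation, that each such lesion is scored PD, and that the design's target ORR does not already allow for the loss. For an individual subject no rate is needed: a single lesion can remove a confirmed response. It is worth correcting because the correction is cheap; it is not evidence that any result was misclassified.

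**What to change.** The change concerns endpoint scoring only. Replace the sentence in Protocol 7.3 with:

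> *New cutaneous lesions judged to be metastases of the study tumor count as RECIST 1.1 progression, with or without imaging. A lesion shown by biopsy to be non-metastatic (for example hyperkeratosis, keratoacanthoma or primary cutaneous squamous cell carcinoma) is not a new tumor lesion. An equivocal lesion is not PD until clarified; if it proves to be metastasis, PD is dated to its first appearance.*

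For squamous study tumors (SCCHN, squamous cervical, squamous NSCLC), add that a squamous carcinoma of the skin is not exempt on its label alone: the IRC decides between primary and metastasis from the pathology report and the physical findings. Put the same text in the IRC charter and send the IRC the reports already kept under 7.1.2.2.

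The protocol already uses both ideas elsewhere: 7.3.2 treats a new liver lesion that fails its criteria as equivocal, and 7.3.3 dates progression back to the scan that first raised the question.

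The cost is a short text change in two documents. Some PD calls will wait for pathology and then be back-dated. Sections 5.1.7.2 and 6.5.4.4 differ on whether every suspicious lesion or one representative lesion is biopsied. They must be reconciled, so that it is clear which lesions will have a pathology result; those without one fall under the equivocal rule.
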